7.5.1.13 Treatment Withdrawal

If the patient is withdrawn from study treatment, the patient should be examined as soon as possible after making the withdrawal decision. Adverse events and use of concomitant medications are captured. Blood and urine are collected for safety laboratory, immunogenicity, HS and PK assessments. When separate consent for future research has been provided, blood and urine are also collected for storage at the central laboratory for future biomarker research, and if the patient is also withdrawn from the study blood is collected for future genetic research. Vital signs are assessed and a neurological and a physical examination are performed. A 12-lead ECG is obtained and an echocardiography is performed. Height, weight and head circumference are obtained. Additional safety assessments will be performed at the discretion of the investigator, as warranted by any AE(s) leading to treatment withdrawal.

When possible, non-infusion-related study assessments should continue in accordance with the Schedule of Events (refer to Table 3) until completion of the Week 24 visit. At minimum, the Early Termination assessments should be repeated 30 to 40 days after the last SOBI003 administration. Patients with ADA-positive samples should continue to be followed in accordance with Sections 7.5.5.3 and 7.5.6.1.

7.5.1.14 Estimated blood sampling volumes and sampling priority list

Applying the European Commission guidance (20), the study-related blood loss should not exceed 3% of the total blood volume during a period of 4 weeks and should not exceed 1% at any single time. Examples of recommended blood draw volume limits per the European Commission guidance are provided in Table 7.

Local and/or regional guidelines regarding blood draw volumes may also apply.

Information of blood volumes per assessment type and sampling occasion are provided in a separate study-specific Laboratory Manual. An overview is presented in Appendix 1.

Blood sampling necessary for the clinical management of the patient will prevail over any study specific sampling.

Should the blood volume be restricted at any of the sampling time points, then the analyses should be prioritized in the following order:

1. Immunogenicity (ADA)
2. Coagulation
3. PK
4. Hematology
5. Blood chemistry
6. HS
7. Blood sample collection for future pharmacogenetics research
8. Serum collection for future biomarker analyses

Table 7 Examples of recommended blood draw volume limits

Patient Weight (kg)	Blood Draw Limits (mL) ^(a)	
	Single Occasion ^(b)	4 weeks ^(c)
10.0	8.0	24.0
15.0	12.0	36.0
20.0	16.0	48.0
25.0	20.0	60.0

a European Commission guidance (20)

b Representing 1% of total blood volume, where total blood volume is estimated to 80 ml/kg body weight

c Representing 3% of total blood volume, where total blood volume is estimated to 80 ml/kg body weight

7.5.2 Medical history

7.5.2.1 MPS IIIA diagnosis

Information on diagnosis date and prior MPS IIIA diagnostic procedures are captured, including assessment date, diagnostic method used, and test result (positive/negative). The following diagnostic methods are of particular interest; urinary glycosaminoglycan (GAG), serum HS, sulfamidase enzyme activity in leucocytes or fibroblasts, and SGSH genotyping. Moreover, information is collected regarding MPS IIIA disease in older siblings and if prenatal diagnosis has been conducted.

At Screening, blood (5 mL) is obtained for SGSH genotyping and extraction of leucocytes for assessments of sulfamidase enzyme activity at a central laboratory (Greenwood Genetic Center). Blood sampling details are provided separately in the Study laboratory manual. The central laboratory results are used for confirmation of the eligibility criteria.

7.5.2.2 Other diagnoses

Information on prior and current other diagnoses obtained within 6 years prior to study enrolment are captured (diagnosis and date of diagnosis), with emphasis on conditions that are frequent in the MPS IIIA population. This includes inguinal and umbilical hernias, cardiac valve disease, epilepsy/seizures, spasticity, congenital joint stiffness, hip dysplasia, scoliosis, kyphosis, lumbar lordosis, carpal tunnel syndrome, trigger digits, joint contractions, autism, hyperactivity or attention deficit disorder (ADD).

7.5.2.3 Other medical conditions

Information on prior and current other medical conditions within 1 year prior to study enrolment are captured (symptom, frequency when applicable and month of onset of most recent episode), with emphasis on conditions that are frequent in the MPS IIIA population. This includes hepatomegaly and/or splenomegaly, ear-nose-throat (ENT) infections, diarrhea, sleep disorder, swallowing/eating difficulties, hearing loss and/or visual acuity problems.

The definition of prior medical conditions includes signs, symptoms, and diagnoses made prior to the informed consent is signed.

The definition of current medical conditions includes all signs, symptoms, and diagnoses made from the time informed consent is signed until completion of the Baseline assessments, i.e., until the first SOBI003 infusion is about to be initiated on Day 1 at Week 1.

7.5.2.4 Prior medical procedures

Information on prior medical procedures performed within 6 years prior to study enrolment are captured (procedure and month/year conducted), with emphasis on conditions that are frequent in the MPS IIIA population. This includes tonsillectomy, adenoidectomy, myringotomy, gastrostomy, and jujenostomy.

7.5.3 Demography

The following demographic data are captured at Screening; date of birth, gestational age at birth, gender, ethnicity, race, country of residence and native language. In addition, information on the patient's siblings is captured, including age and MPS IIIA diagnostic status (confirmed as non-affected/confirmed as affected/under current investigation). For sibling(s) with confirmed diagnosis, the sibling's age at diagnosis and genotype are also captured, when known.

7.5.4 Efficacy assessments

7.5.4.1 Adaptive behavior

The VABS-II is assessed at Screening, Baseline (within 2 weeks prior to first SOBI003 infusion) and at Week 24. The screening assessment is used to determine patient eligibility in terms of developmental age.

The patients' ability to cope with changes, to demonstrate independence and to learn new skills are assessed by use of the Expanded Interview Form of the VABS-II. This measures five competence domains: communication, socialization, daily living skills, motor skills and an adaptive behavior composite of the first four domains.

The VABS-II is assessed by parent/caregiver interviews performed by child development specialists/psychologists with prior experience of MPS IIIA patients. Prior to study initiation, additional study-specific assessment training is provided in order to reduce between-site variability. Every effort will be made to have the same parent/caregiver interviewed at each assessment time point (i.e., at Screening, Baseline and Week 24). In addition, each patient's parent/caregiver should preferably have the same interviewer throughout the study in order to reduce potential variability.

The developmental age at Screening is determined as the mean of the subdomain age-equivalent scores including the communication, socialization, daily living skills, and motor skills domains.

The adaptive behavior age-equivalent score is determined as the mean of the subdomain age-equivalent scores including the communication, socialization, and daily living skills (thus, excluding the motor skills domains).

Completed assessment forms will be sent to a central reader (NeuroCog Trials), for data quality assurance of completed assessment forms, calculation of final scores and determination of Age Equivalence scores, and data management.

7.5.4.2 Neurocognition

Neurocognition is assessed at Baseline (within 2 weeks prior to first SOBI003 infusion) and at Week 24, by use of the neurocognition domain of the BSID-III and/or the KABC-II Nonverbal Index (NVI).

The patient's chronological age in combination with the patient's adaptive behavior age-equivalent score as established by VABS-II, will determine which neurocognitive test(s) to apply. The algorithm in Table 8 is applied and the test(s) administered at Baseline should also be used at Week 24.

Table 8 Selection of neurocognitive assessment method

Chronological age at the assessment time point	VABS-II adaptive behavior age-equivalence	Neurocognitive test to apply
<42 months	Any age-equivalence	BSID-III
≥42 months	<36 months	BSID-III
≥42 months	36 to 42 months	BSID-III + KABC-II*
≥42 months	>42 months	KABC-II

* The BSID-III should be administered first, and there should be at least 2 days until the KABC-II assessment in order to reduce KABC-II outcome bias of patient tiredness.

The neurocognitive developmental age (months) is derived on the basis of the BSID-III cognitive total raw score and BSID-III age-normative data.

The neurocognitive developmental age (months) is derived from the mean AEQ scores on the NVI of the KABC-II.

The Development Quotient (DQ) is obtained by dividing the neurocognitive developmental age with chronological age.

Neurocognition assessments are performed by child development specialists/psychologists with prior experience of MPS IIIA patients. Prior to study initiation, additional study-specific assessment training is provided in order to reduce between-site variability.

Each patient should preferably have the same assessor throughout the study in order to reduce within-patient variability. Attempts should be made to have the assessments made at least 5 days after any anesthesia/sedation. When practically feasible, the aim should be to have the assessments performed in rested children early during the day, i.e., prior to 1 pm. The aim should also be to roughly keep the same assessment time point for an individual child, i.e., morning/afternoon.

To ensure that the BSID-III and KABC-II assessments are performed in accordance with the study instructions, completed assessment forms will be sent to a central reader (NeuroCog Trials) for data quality assurance, calculation of final scores and determination of Age Equivalence scores.

7.5.4.3 Language

Language is assessed at Baseline and at Week 24.

Expressive and receptive language are assessed by the BSID-III language module and the VABS-II communication domain. In addition, written language is assessed by the VABS-II communication domain.

For those patients taking the KABC-II for cognitive assessment, the Expressive Vocabulary from the KABC-II will be applied to assess language development.

7.5.4.4 Motor function

Motor function is assessed at Baseline and at Week 24.

Fine and gross motor skills are assessed by the BSID-III motor function module and the VABS-II motor skills domain.

7.5.4.5 Sleep pattern

The patients' sleep pattern is evaluated using the CSHQ and by use of actigraphy.

Two additional items are added to the original CSHQ questionnaire to further characterize common MPS IIIA specific issues with sleep, i.e., disruptive behavior at night and dangerous behavior at night. The CSHQ is completed by the primary caregiver at Baseline and prior to the infusions at Weeks 12 and 24. This CSHQ will capture the child's sleep habits during the past week. Every effort will be made to have the same caregiver completing the CSHQ at each assessment time point.

An actigraph (ActiGraph GT9X Link) will be applied to the non-dominant wrist or ankle and recordings will be made for 7 consecutive days and nights at Baseline and at Weeks 11 and 23. The wrist or ankle placement should be used consistently throughout the study. At Baseline, the aim should be to have the recording completed prior to any anesthesia/sedation is applied and prior to blood samplings. At Weeks 11 and 23, the aim should be to have the recordings completed prior to the SOBI003 infusions on Day 1 at Weeks 12 and 24.

The device will be worn constantly during the recording periods only allowing removal for washing and bathing. The aim is to ensure that at least 5 days of evaluable recordings are obtained on each occasion. A daily wear time of 20 hours per day will be regarded as a compliant recording. The recording will be supported by an actigraph log. Recorded actigraph data will be evaluated using the accompanying software developed by the manufacturer. A subset of the actigraphy data is coded to be analyzed in a subsequent separate blinded analysis of the manually edited dataset.

The following parameters will be determined on the basis of recordings in the actigraph log:

- Bedtime (Clock time child is put to bed)
- Wake time (Clock time of child is taken out of bed)
- Time in bed (Time between Bedtime and Wake time)

The following variables are derived as obtained from the actigraph software:

- Sleep onset (Clock time for first appearance of a predetermined number of consecutive min of sleep)
- Sleep offset (Clock time for last of a predetermined number of consecutive min of sleep)
- Sleep period (Time between sleep onset and sleep offset)
- Total sleep time (TST, Duration of sleep in sleep period)
- Wake after sleep onset (WASO, number of minutes scored as wake during sleep period)
- Sleep efficiency (Percentage sleep: TST/time in bed)
- Night waking frequency (number of night wakings)
- Night waking duration (Sum of minutes scored as night waking)
- 24 h sleep duration (amount of sleep in a 24-h period)

Sleep onset latency is determined as Time between bedtime (as recorded on the actigraph log) and sleep onset (as captured by the actigraph software)

The Sadeh algorithm (25) is used for determining which epochs (1-minute recordings) are marked as “sleep” versus which are marked as “awake”. The Tudor-Locke method is applied to determine sleep periods, where 5 consecutive minutes of recorded “sleep” defines Sleep onset and where 10 consecutive minutes of “awake” time defines Sleep offset.

7.5.4.6 Magnetic resonance imaging

MRI scanning protocols including details on sequence parameters and scanning guidelines are provided to the clinical sites under the coordination of the central MRI reader. MRI field strength should be a minimum of 1.5, preferable, 3.0 tesla.

Preferably, the same MRI technician should perform all study related scans. The separate MRI assessment protocol provided prior to the study start should be followed for each scan. Study specific training is provided and test scans will be reviewed by the central MRI reader prior to initiation of any study assessments at the site.

Brain and abdominal MRI are performed under general anesthesia at Baseline and Week 24. MRI data are sent to the central reader for quantitative analyses.

The brain MRI assessment protocol includes:

1. 3D T1-weighted MPRAGE (~6 min) for volumetric analysis
2. DTI and gre fieldmap (~10 min) for white matter analysis
3. 3D FLAIR and T2 (~8 min) for volumetric analysis
4. 4.SWI (~10 min) for iron content analysis

The abdominal MRI assessment protocol includes:

1. T1 3D VIBE (~2 min.)
2. T2 HASTE (~2 min.)

Liver /spleen volumes are evaluated by MRI using a standard MRI protocol.

7.5.4.7 Quality of life and caregiver burden

The parent proxy-report format of the PedsQL questionnaire (Version 4.0 [26]) will be used to assess the child’s quality of life. The Family impact Module of the PedsQL (Version 2.0) will be used to assess the caregiver burden. The PedsQL will be completed at Baseline and at Weeks 12 and 24. Every effort should be made to have the same parent/caregiver responding to the PedsQL questions at each assessment time point (i.e., at Baseline and Weeks 12 and 24).

The PedsQL version (i.e., infant/toddler/young children) will be selected on the basis of the chronological age of the patient.

7.5.5 Safety assessments

7.5.5.1 Adverse events

7.5.5.1.1 Definitions

Adverse event

An Adverse event (AE) is any untoward medical occurrence in a patient or trial subject administered a pharmaceutical product; the event does not necessarily have a causal relationship with the treatment or usage.

Adverse events include the following:

- Abnormal test findings, as specified below.
- Clinically significant signs and symptoms.
- Changes in physical examination findings.
- Unexpected progression/worsening of underlying disease.

In addition, signs and symptoms resulting from the following should also be handled according to the same principles as Adverse Events:

- Overdose.
- Withdrawal of treatment.
- Interactions.
- Abuse.
- Misuse.

Abnormal test findings

An abnormal test finding, e.g. abnormal laboratory analysis results, vital signs or ECG, should be recorded as an Adverse Event in any of the following situations:

- The test is associated with accompanying symptoms. Note, that the symptom, not the test result, should be recorded as an AE.
- The test result leads to a medical/surgical intervention including withdrawal of IMP(s) or discontinuation from the study. Repeat/confirmatory testing is not considered a medical intervention.
- The investigator considers the test result to be clinically significant.

Preexisting conditions

A preexisting condition (i.e., a disorder present before the adverse event reporting period started and noted on the pretreatment medical history/physical examination form) should not be reported as an adverse event unless the condition worsens or episodes increase in frequency during the adverse event reporting period.

Procedures

Diagnostic and therapeutic non-invasive and invasive procedures, such as surgery, should not be reported as adverse events. However, the medical condition for which the procedure was performed should be reported if it meets the definition of an adverse event. For example, an acute appendicitis that begins during the adverse event reporting period should be reported as the adverse event and the resulting appendectomy entered in the comments section of the CRF.

Serious adverse event (SAE)

An adverse event that meets one or more of the following criteria/outcomes is classified as serious:

- Results in death.
- Is life-threatening (i.e., at immediate risk of death).
- Requires in-patient hospitalization or prolongation of existing hospitalization.
- Results in persistent or significant disability/incapacity.
- Is a congenital anomaly/birth defect (i.e., in an offspring to the study subject).

Other medically important adverse events that may not result in death, be life threatening, or require hospitalization may be considered serious when, based upon appropriate medical judgment, they may jeopardize the patient or subject or may require medical or surgical intervention to prevent one of the outcomes listed above. Examples of such events are intensive treatment in an emergency room or at home for allergic bronchospasm, blood dyscrasias or convulsions that do not result in hospitalization or development of dependency or abuse.

Serious also includes any other event that the investigator or company judges to be serious. Any suspected transmission of an infectious agent via IMP shall also be considered serious.

Hospitalization

Hospitalization includes transfers within a hospital (e.g. from the hospital ward to the intensive care unit) and also includes admissions less than 24 hours. The following situations are not considered hospitalizations (although other SAE criteria may still apply):

- Outpatient procedures / ambulatory care.
- Emergency department visits.

Hospitalization in the absence of an adverse event occurring during the study should not be considered an SAE. This includes:

- Hospitalization due to a pre-existing condition not associated with a worsening of the pre-existing condition.
- Protocol specified admission.
- Elective admission, e.g. due to cosmetic surgery.
- Pre-planned admission for a condition specified at Baseline for the patient.

[figure not shown]
Treatment-emergent adverse event (TEAE)

TEAE is any AE with onset or worsening reported from the time that the first dose of IMP is administered until completion of or withdrawal from the study.

7.5.5.1.2 Adverse event reporting period

The period for recording adverse events, including SAEs, on the CRF begins upon receiving the first dose of investigational medication and ends at completion of the Week 24 visit.

In addition, SAEs should be reported, from the time the ICF is signed until 28 days past the last dose of IMP. Furthermore, any SAE should be reported to Sobi irrespective of the time of occurrence if a causal relationship between the event and the IMP(s) is suspected.

7.5.5.1.3 Eliciting and recording adverse event information

The investigator is to record all directly observed adverse events, and all adverse events spontaneously reported by the parent/patient, in the CRF using concise medical terminology.

When possible and appropriate, a diagnosis rather than individual signs and symptoms shall be recorded. The investigator is responsible for obtaining sufficient information to determine seriousness, causality and outcome of each adverse event.

Severity assessment

For the purpose of consistency, the investigator will use the grading provided in Table 9 to describe the maximum intensity of the adverse event. The grading is based on the NCI CTCAE (version 4.03).

Table 9 Severity grade definitions according to NCI CTCAE (version 4.03)

Grade I	Mild; asymptomatic or mild symptoms; clinical or diagnostic observations only; intervention not indicated
Grade II	Moderate; minimal, local or non-invasive intervention indicated; limiting age-appropriate instrumental Activities of Daily Living (ADL)
Grade III	Severe or medically significant but not immediately life-threatening; hospitalization or prolongation of hospitalization indicated; disabling; limiting self-care ADL
Grade IV	Life-threatening consequences; urgent intervention indicated

Note the distinction between the seriousness (serious/non-serious) and the intensity (severity) of an adverse event. **Severe** is a measure of intensity; thus, a **severe** reaction is not necessarily a **serious** reaction. For example, a headache may be severe in intensity, but would not be classified as serious unless it met one of the criteria for serious events listed above.

Causality assessment

For each adverse event, the investigator or sub-investigator must make a causality assessment on the basis of his/her clinical judgment to determine if there is a reasonable possibility that the IMP(s) caused the adverse event. The adverse event is assessed as related or not related to the IMP(s) with the following definitions:

Related

The AE follows a reasonable temporal sequence from the study product administration, and cannot be reasonably explained by the subject's clinical state or other factors (e.g., disease under study, concurrent diseases, or concomitant medications).

Not Related

The AE does not follow a reasonable temporal sequence from study product administration, or can be reasonably explained by the subject's clinical state or other factors (e.g., disease under study, concurrent diseases, and concomitant medications).

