7.5.5.9.1 Stopping rules

In the context of this study, the term toxicity means clinically significant drug related adverse reaction(s). In case of serious toxicity defined as a Grade III-V SAE, an *ad hoc* SRC meeting will be held within 24 hours after Sobi awareness of the adverse event. SRC will decide on the impact on an individual, cohort or entire study level, continue trial unchanged, continue trial with modifications, or to put the trial on hold.

Standard toxicity grading according to the NCI CTCAE are used to grade AEs and to decide on suspension level.

- The study will be halted if a patient develops a Grade IV-V SAE suspected to be IMP related.
- The treatment arm will be halted if at least 2 out of 3 patients in the same cohort experience a similar drug-related Grade III SAE.
- Study treatment will be discontinued on an individual level if assessment by an *ad hoc* SRC or the investigator conclude significant risk to the subject's safety.

If at least 2 out of 3 patients in the same cohort experience a drug-related Grade III AE in different organ systems, the SRC will base the dose level selection for the next cohort(s) on the nature of the adverse events observed. An *ad hoc* DMC meeting may be held to provide recommendation if requested by the SRC.

Toxicity grade definitions according to NCI CTCAE (version 4.03)

Grade I	Mild; asymptomatic or mild symptoms; clinical or diagnostic observations only; intervention not indicated
Grade II	Moderate; minimal, local or non-invasive intervention indicated; limiting age-appropriate instrumental Activities of Daily Living (ADL)
Grade III	Severe or medically significant but not immediately life-threatening; hospitalization or prolongation of hospitalization indicated; disabling; limiting self-care ADL
Grade IV	Life-threatening consequences; urgent intervention indicated
Grade V	Death related to AE

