An Infusion related reaction (IRR) has been defined as any AE occurring during an infusion or within 24 hours after end of infusion and which is considered related to SOBI003 treatment as judged by the investigator. IRRs may appear as symptoms such as rash, urticaria, erythema, emesis, loose stools, fever, alterations in heart rate, and blood pressure, but could also include other symptoms considered related to the infusion. Such symptoms (by PT and SOC) will be grouped into separate IRRs. There can be one IRR per infusion, in case several IRR symptoms are reported for one infusion they will be counted as one single IRR.

TEAEs will also be classified according to the patients ADA status (positive, negative, boosted, unknown) at the time of the AE occurrence.

All AEs will be summarized by dose cohort. The following analyses will be performed:

- Overall summary of AEs (overall, non-treatment emergent SAEs, TEAEs, drug-related TEAEs, non-serious TEAEs, serious TEAEs, serious drug-related TEAEs, TEAEs leading to study and/or treatment withdrawal, drug-related TEAEs leading to study and/or treatment withdrawal, serious TEAEs leading to study and/or treatment withdrawal, TEAEs leading to death, IRRs)
- Overall summary of IRRs (overall, serious IRRs, IRRs leading to study and/or treatment withdrawal). There can be one IRR per infusion, in case several IRR symptoms are reported for one infusion they will be counted as one single IRR.
- TEAEs by SOC and PT
- TEAEs by SOC and PT and by maximum CTCAE grade
- Drug-related TEAEs by SOC and PT
- Drug-related TEAEs by SOC and PT by maximum CTCAE grade
- Serious TEAEs by SOC and PT
- Serious TEAEs by SOC and PT by maximum CTCAE grade
- Serious drug-related TEAEs by SOC and PT
- Serious drug-related TEAEs by SOC and PT by maximum CTCAE grade
- TEAEs leading to study and/or treatment withdrawal by SOC and PT
- TEAEs leading to study and/or treatment withdrawal by SOC and PT by maximum CTCAE grade

- Drug-related TEAEs leading to study and/or treatment withdrawal by SOC and PT
- Drug-related TEAEs leading to study and/or treatment withdrawal by SOC and PT by maximum CTCAE grade
- TEAEs by SOC and PT and by ADA status
- IRR symptoms by SOC and PT
- IRR symptoms by SOC and PT by maximum CTCAE grade
- Serious IRR symptoms by SOC and PT
- Serious IRR symptoms by SOC and PT by maximum CTCAE grade
- IRR symptoms leading to study and/or treatment withdrawal by SOC and PT

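### The Related / Not Related definitions in Protocol 7.5.5.1.3 are narrower than the reasonable-possibility test they are meant to apply, so related events can only be under-counted

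*Protocol*

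**What the plan says.** Under causality assessment, Protocol 7.5.5.1.3 asks the investigator to "determine if there is a reasonable possibility that the IMP(s) caused the adverse event". Only two answers are allowed, and each is defined.

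- *Related* has this wording: "The AE follows a reasonable temporal sequence from the study product administration, and cannot be reasonably explained by" factors apart from the product, such as the child's own condition.
- *Not Related* has this wording: "The AE does not follow a reasonable temporal sequence from study product administration, or can be reasonably explained by" that same set of factors. The examples given are the disease under study, concurrent diseases and concomitant medications.

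Several later provisions use the answer. In Protocol 7.5.5.9.1, toxicity means drug-related reactions, and both rules on Grade III events in 2 of 3 patients count drug-related events. The top-level rule is worded differently: "The study will be halted if a patient develops a Grade IV-V SAE suspected to be IMP related". Protocol 7.5.5.1.5 extends follow-up beyond study participation for events assessed as related. SAP 14.2 plans a set of drug-related TEAE tables and defines an IRR by its timing plus a causal condition: an event "which is considered related to SOBI003 treatment as judged by the investigator". Where a TEAE has no causality assessment, SAP 14.2 counts it as drug-related.

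**The concern.** The stated question and the definitions give different answers for one kind of event: plausible timing, another reasonable explanation, and SOBI003 still a reasonable possibility. The question points to related; the definitions require *Not Related*.

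Such events are foreseeable. SAP 14.2 lists fever, vomiting, loose stools, rash and changes in heart rate or blood pressure as possible IRR symptoms. Protocol 7.5.2.3 names diarrhea and ENT infections among conditions frequent in MPS IIIA. Study anesthesia or sedation is scheduled on the day after the Week 12 and Week 24 infusions. Meanwhile, Protocol 5.3 identifies hypersensitivity and infusion reactions as a known hazard of this class of therapy.

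The trial has no control group against which background events could be set, so the attribution label carries more weight than it would in a randomized study. A label that errs in one direction makes the product look better tolerated in every table that depends on it.

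**Working it through.** The plan states no figure on this point, so the check is one of logic.

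**Step 1: what the definitions do.** Let T mean plausible timing and A mean that another reasonable explanation exists.

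- Related = T and not A.
- Not Related = not T, or A.

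These are exact complements. Every event receives one label and there is no middle category.

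**Step 2: comparison with the stated question.**

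| Timing plausible | Other explanation | Label under definitions | Reasonable possibility of SOBI003? |
|---|---|---|---|
| Yes | No | Related | Yes |
| Yes | Yes | Not Related | May be yes: the conflict |
| No | No | Not Related | Ordinarily no |
| No | Yes | Not Related | Ordinarily no |

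Every event labelled *Related* also meets the reasonable-possibility test. Some events that meet the test are labelled *Not Related*. The related count is therefore less than or equal to the count under the stated test, whatever the data.

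**Step 3: whether anything else repairs it.** The worst-case rule in SAP 14.2 applies only when causality is missing. It does not reclassify an event already recorded as *Not Related*. A blank field thus counts as related, while an assessed event with two reasonable causes does not.

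**Step 4: what depends on the label.**

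| Item | Depends on | Affected |
|---|---|---|
| Arm halt, 2 of 3 with similar Grade III SAE (7.5.5.9.1) | Drug-related | Yes |
| Next-cohort dose selection, 2 of 3 with Grade III AE in different organ systems (7.5.5.9.1) | Drug-related | Yes |
| Drug-related TEAE tables (SAP 14.2) | Related | Yes |
| IRR tabulation (SAP 14.2) | Timing and related | Yes |
| Post-study follow-up of related AEs (7.5.5.1.5) | Related | Yes |
| Grade IV-V study halt (7.5.5.9.1) | Suspected, not defined | Unclear |
| Individual discontinuation (7.5.5.9.1) | Risk to the patient | No |
| Primary endpoint, TEAEs and SAEs (6.1.1) | All causality | No |
| Investigator SAE reporting (7.5.5.1.4) | All causality | No |

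**The case against.** The strongest reply is that safety oversight does not rest on this label, and much of that stands. The primary endpoint is all-causality. Every SAE is reported whatever its cause. The SRC data package in Protocol 7.5.5.9 has no relatedness filter, and any principal investigator or sponsor SRC member can call an extra meeting. The staggering reviews in 7.1 and the DMC do not require a *Related* entry. AEs that lead to treatment withdrawal are followed to resolution or stability under 7.3.3.2. SAP 14.2 also tabulates all TEAEs by maximum grade. Finally, 7.5.5.1.3 appeals to clinical judgment, so some investigators may have applied the broader test in practice. None of this reconciles the two tests or restores events missing from the tables that use the label.

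A reader might be tempted to go further in four ways, which the documents do not support.

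- **That an endpoint is biased.** IRR is not an endpoint in Protocol section 6 or SAP 3.4. It is a safety tabulation.
- **That the Grade IV-V halt or expedited reporting is weakened.** The halt turns on suspicion, which may be broader than *Related*. The expedited-reporting text speaks of adverse reactions without naming the investigator's two-way label.
- **That two-cause events are the typical case.** No frequency is given. Study anesthesia can compete as an explanation at no more than 2 of the 24 infusions. Pre-existing conditions become AEs only on worsening or increased frequency.
- **That the loss can be sized.** Suppose a share q of true reactions were labelled *Not Related*, independently. With q = 0.3, purely an assumption, the 2-of-3 rule would still be met with probability 0.7² = 0.49 if exactly two patients reacted, but 0.7³ + 3 × 0.7² × 0.3 = 0.78 if all three did. An IRR with two symptoms would vanish only if both were relabelled: 0.3² = 0.09. The answer depends on q, the number of reactors, independence and symptoms per infusion, and the documents give none of these.

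**Conclusion.** The inconsistency is real and should be resolved. Its direction follows from the wording alone: the definitions can remove related events but cannot add any. This assumes that investigators applied the definitions as written. Its size cannot be derived from the documents and may be small.

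The reach is limited to the two drug-related Grade III rules, the drug-related TEAE tables, the IRR tabulation and post-study follow-up of related events. Whether it extends to the Grade IV-V halt cannot be settled while suspicion is left undefined.

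Timing also limits what can now be gained. SAP 4.1 records that the program was discontinued, with three patients in each of Cohorts 1 and 2, all enrolled in the extension study, and that Cohort 3 will not start. No escalation decision in this study remains to be protected. What remains is the clinical study report, where related-event and IRR counts from six children will be read as a tolerability profile.

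**What to change.** **SAP 14.2, the main remedy for this report.** Beside the IRR symptom tables, add a table of all AEs with onset from infusion start to 24 h after infusion end, regardless of causality, by cohort, SOC, PT and maximum grade. The IRR definition already needs this window, so the new table only removes the causal condition. Protocol 7.5.6.1 has infusion start and completion times recorded. At symptom level, the two tables bracket the answer: the number of events in the window that meet the reasonable-possibility test lies between the IRR symptom count and the all-causality count. State in the SAP which causality standard the related labels follow.

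**Protocol 7.5.5.1.3.** Align the definitions with the question asked:

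- *Related*: plausible timing and a reasonable possibility that SOBI003 caused or contributed to the event, even if another cause is also possible.
- *Not Related*: timing is not plausible, or another cause accounts for the event so that no reasonable possibility of a SOBI003 contribution remains.

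Also reconcile the term suspected in 7.5.5.9.1 with these definitions. No stopping threshold needs to change for this.

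**Cost.** The SAP part is one extra table from data already collected. The protocol part is a wording change, carried into the CRF instructions. It reclassifies nothing already recorded, so it helps only prospectively or if investigators re-assess the recorded events, which would take site time and be done with outcomes known. The downside is a somewhat higher count of related events under the aligned definitions. The new table will also include events that have nothing to do with SOBI003, and its title should say so.
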